4.2 Design Diagram

[figure not shown]
This randomized, double-blind, double-dummy, placebo controlled, parallel design study compares two different dose regimens of risankizumab with placebo. In total, approximately 168 patients with moderate to severe chronic plaque psoriasis will be randomized in this trial.

Patients are randomized at a ratio of 2:2:1:1 to one of 4 treatment arms (risankizumab 75 mg, risankizumab 150 mg, placebo switching to risankizumab 75 mg after Week 16, and placebo switching to risankizumab 150 mg after Week 16) as shown in [Figure 1](#).

Randomization will be stratified by concomitant PsA at baseline (Yes versus No) and body weight (≤ 90 kg versus > 90 kg).

Patients will be offered to roll over into an extension trial, if they have completed the study and meet the inclusion criteria for the extension trial.

Figure 1. Study Design Schematic

BI 655066 is risankizumab.

4.3 Sample Size

For the Japanese submission, the safety data of at least 100 Japanese patients exposed to risankizumab at the registered dose(s) for 1 year or more is necessary for long team safety assessment as a result of the PMDA consultation meeting in 2015. This study will enroll a total of 168 patients, with 56 patients in each of the two risankizumab arms and 56 patients in the placebo arm. It is expected that at least 68 patients exposed to risankizumab 75 mg and 68 patients exposed to risankizumab 150 mg will reach at least 1 year exposure to risankizumab in this clinical trial or in the following extension study. Other global phase 3 trials where Japanese patients are to be enrolled will make up for the remaining safety data requirements.

Based on the outcome from the Trial 1311.2, the PASI 90 response rate at Week 16 is assumed to be at least 65% in each of the risankizumab arm. The phase 3 results from ustekinumab and secukinumab indicate a response rate for PASI 90 of approximately 5% in the placebo arm. With hieratical order of testing the 150 mg risankizumab vs placebo followed 75 mg risankizumab vs placebo, the above sample size will provide more than 90% power to detect the superiority of both risankizumab arms vs placebo.

4.4 Interim Analysis

Before the submission to regulatory agencies with the long-term data, an interim report will be prepared for the submissions analysis pertaining to Part A. Primary endpoint (PASI 90 score at Week 16) for all patients will be included in the Week 28 analyses, which is the only and final analysis for the primary endpoint; hence no alpha adjustment is required. For this analysis all efficacy endpoints and safety as well as PK and immunogenicity data will be analysed. As endpoints for Week 28, same analyses will be performed for the Week 52 endpoints defined in Section 10.3.

AbbVie Data and Statistical Sciences will be unblinded to perform this analysis. Unblinded treatment assignments will not be disseminated to BI, the sites, investigators, or patients until the end of final database lock.

5.0 Analysis Populations and Stratification

5.1 Analysis Populations

In this SAP, Part A refers to Week 0 to Week 16, and Part B refers to Week 16 and after.

Intent-to-Treat (ITT) Population: The ITT Population is defined as all subjects who are randomized at Week 0. ITT Population will be used for the efficacy analyses in Part A and Part B, as well as efficacy across the entire study (cross-period) for subjects who are randomized to risankizumab arms. Subjects who are randomized to placebo in Part A and do not continue into Part B will be excluded from the analysis in Part B.

ITT Population will be analyzed by treatment group as randomized.

Per-Protocol (PP) Population: To evaluate the impact of protocol deviations on the primary endpoint, additional efficacy analyses will be performed on a PP Population. The PP Population will include those who were most compliant with the protocol in ways that could impact the primary endpoints. Final results and the criteria for exclusion of subjects will be finalized prior to database lock.

The PP Population is defined as all subjects from the ITT Population who meet all the following criteria:

- Subjects must receive at least 75% of planned study drug injections (including dummy placebo injections) in Part A (prior to Week 16).
- Subjects must have at least one PASI assessment post-baseline.
- Inclusion Criterion 2: Subjects must have stable moderate to severe chronic plaque psoriasis at baseline:
 - Have an BSA $\geq 10\%$ and
 - Have a PASI ≥ 12 and
 - Have an sPGA ≥ 3 .

Final results and the criteria for exclusion of subjects will be finalized prior to the interim database lock.

PP Populations will be analyzed by treatment group as randomized.

Safety Population: Safety analyses will be performed on a Safety Population, comprising all randomized participants who received at least one dose of study drug in Part A. The safety analysis will be performed based on the actual treatment received at the randomization visit. Subjects who do not continue into Part B will be excluded from the Part B specific safety analysis. All safety analyses will be conducted on the Safety Population.

All Risankizumab Treated (ALL_RZB) Population: The ALL_RZB Population is defined as subjects who receive at least one dose of risankizumab in the study. Key safety summaries will be provided on the ALL_RZB Population.

Table 1. Notation for Treatment Groups

Population	Treatment Code	Definition
ITT/Safety (Part A)	RZB_75	Subjects who randomized to risankizumab 75 mg.
	RZB_150	Subjects who randomized to risankizumab 150 mg.
	PBO	Subjects who randomized to either of the two placebo arms.
ITT/Safety (Part B)	RZB_75/RZB_75	Subjects who randomized to risankizumab 75 mg.
	RZB_150/RZB_150	Subjects who randomized to risankizumab 150 mg.
	PBO/RZB_75	Subjects who randomized to placebo and then risankizumab 75 mg entered Part B
	PBO/RZB_150	Subjects who randomized to placebo and then risankizumab 150 mg entered Part B
ITT/Safety (entire study)	RZB_75/RZB_75	Subjects who randomized to risankizumab 75 mg.
	RZB_150/RZB_150	Subjects who randomized to risankizumab 150 mg.
ALL_RZB	ALL_RZB	Subjects who received at least one dose of risankizumab 75/150 mg.

5.2**Variables Used for Stratification of Randomization**

Randomization will be stratified by concomitant PsA at baseline (Yes versus No) and body weight (≤ 90 kg versus > 90 kg).

6.0**Analysis Conventions****Definition of Baseline**

The last non-missing observation collected on or before the date of the first dose of study drug injection will be used as Baseline for summary of demographics and disease characteristics, safety and efficacy analyses, with the exception that:

- The last evaluation on or prior to the date of first dose of risankizumab will be used for the safety analyses in Part B among subjects randomized to placebo at Week 0, and the safety analyses in the ALL_RZB Population.
- For all vital sign assessments, only assessments prior to first dose time will be considered, since vital signs are to be assessed both pre- and post-dose in some visits.

Entry of Part B is defined as the last non-missing observation collected on or before the date of the first dose of study drug in Part B for PBO/RZB_75 and PBO/RZB_150 arms and last non-missing observation collected on or before the date of Week 16 visit for RZB_75/RZB_75 and RZB_150/RZB_150 arms.

Definition of Final Observation (Applicable to Safety Analyses)

Final observation in Part A is defined as the last non-missing observation collected within 105 days following the last dose of study drug in Part A for those who do not enter Part B, and on or before the first dose date of study drug injection in Part B for subjects who entered Part B. For vital sign assessments, only assessments prior to the first dose of study drug injection in Part B will be included in the analysis for Part A.

Final observation for Part B is defined as the last non-missing observation collected within 105 days following the last dose in Part B.

Final observation for the entire study analyses is defined as the last non-missing observation collected within 105 days following the last dose of study drug.

Final observation for ALL_RZB Population is defined as the last non-missing observation collected within 105 days following the last dose of risankizumab.

Definition of Rx Days in Each Period (Days Relative to the Date of First Dose of Study Drug in Each Period)

Rx Days are calculated for each time point relative to the date of first dose of study drug. They are defined as the number of days between the day of the first dose of study drug and the specific time point. Rx Days are negative values when the time point of interest is prior to the first study drug dose day. Rx Days are positive values when the time point of interest is on or after the first study drug dose day. The day of the first dose of study drug is defined as Rx Day 1, while the day prior to the first study drug dose is defined as Rx Day –1 (there is no Rx Day 0).

Rx Days for Part A and entire study will be defined relative to the date of first dose of study drug. Rx days for Part B will be defined relative to the date of the date of the first study drug injection on or after Week 16.

Definition of Analysis Windows

All time points and corresponding time windows are defined based on Rx Days. The visit schedule with accompanying details can be found in Flow Chart and Section 6.1 of the protocol.

For efficacy analyses, local tolerability, ECG, laboratory parameters, and vital sign variables, analysis windows are constructed using the following algorithm:

- Determine the nominal Rx day for each visit (e.g., Week 4 [4 weeks after Baseline visit] equals Rx Day 29).
- In order to include all post baseline data, the first post-baseline interval starts on the first day after the first dose of study drug (Rx Day 2).

- Determine the window around a specific nominal Rx day by adding or subtracting half of the interval between adjacent visits (e.g., days between Week 4 and Week 8 is 28). The threshold between adjacent visits is determined by splitting the interval evenly between the visits. If the resulting split is between Rx days, then the threshold is determined as the midpoint between the adjacent visits. If the resulting split is on an Rx day, then the threshold is determined as being between that Rx day and the Rx day prior to it (e.g., the split between Week 4 and Week 8 would be between Rx Days 43 and 44).
- If more than one assessment is included in a time window the assessment closest to the nominal day will be used. If there are two observations equidistant to the nominal day, the later one will be used in analyses. If more than one assessment is included on the same day, then the worst assessment on that day will be used in analyses, except those specified in Section 11.0.

The following analysis windows have been specified for the analysis of efficacy, laboratory parameters, and vital signs, etc. for each analysis period. In order to include all post baseline data, the first post baseline interval starts on the day after the date of first study drug injection in each period (Rx Day 2) for all efficacy variables.

For subjects who were randomized and not dosed date of randomization will be used for determining window definitions.

Table 2.
Visit Windows for Analysis of PASI, Vital Signs, and Local Tolerability in Part A (ITT/PP/Safety Populations)

Window Label	Target Day	Interval
Baseline	1	$\leq 1^a$
Week 4	29	[2, 43]
Week 8	57	[44, 71]
Week 12	85	[72, 99]
Week 16	113	[100, 127 ^b]

Rx Day calculated relative to first dose date of study drug. For subjects randomized but not dosed, Rx Day calculated relative to Randomization.

- a. There is no baseline for local tolerability measurements. If time is collected in vital signs, restrict to records prior to the first dose of study drug.
- b. The minimum of upper bound and the day of the first dose date in Part B (and within 105 days of last dose for safety analyses).

Table 3.
Visit Windows for Analysis of Safety Laboratory Tests in Part A (Safety Population)

Window Label	Target Day	Interval
Baseline	1	≤ 1
Week 8	57	[2, 85]
Week 16	113	[86, 141*]

Rx Day calculated relative to first dose date of study drug.

* The minimum of upper bound, the day of the first dose date in Part B, and 105 days of last dose.

Table 4.
Visit Windows for Analysis of ECG in Part A (Safety Population)

Window Label	Target Day	Interval
Baseline	1	≤ 1
Week 4	29	[2, 71]
Week 16	113	[72, 155*]

Rx Day calculated relative to first dose date of study drug.

* The minimum of upper bound, the first dose date in Part B, and the last dose + 105 days.

Table 5. Visit Windows for Analysis of sPGA, PSS, DLQI, HAQ-DI, Pain VAS, Investigator's Global Assessment VAS, Patient's Global Assessment VAS, CRP as an ACR 20 Component, SJC, and TJC in Part A (ITT Population)

Window Label	Target Day	Interval
Baseline	1	≤ 1
Week 16	113	[2, 225*]

Rx Day calculated relative to first dose date of study drug. For subjects randomized but not dosed, Rx Day calculated relative to Randomization.

* The minimum of upper bound and the day of the first dose date in Part B.

Table 6. Visit Windows for Analysis of PASI, Vital Signs, and Local Tolerability in Part B (ITT/Safety Population)

Window Label	Target Day	Interval
Entry of Part B	1	$\leq 1^a$
Week 22	43	[2, 64]
Week 28	85	[65, 106]
Week 34	127	[107, 148]
Week 40	169	[149, 190]
Week 46	211	[191, 232]
Week 52	253	[233, 267]
Week 56	281	[268, 295 ^b]

Rx Day calculated relative to the first dose date on or after Week 16 for PBO/RZB_75 and PBO/RZB_150 arms, and relative to the date of Week 16 visit for RZB_75/RZB_75 and RZB_150/RZB_150 arms. PASI only evaluated from Week 22 to 52. Local tolerability only evaluated from Week 22 to 40.

a. If time is collected for vital sign, restrict to records prior to the first dose of study drug in Part B.

b. The minimum of upper bound and 105 days after the last dose.

Subjects who enter the Open Label Extension Study 1311.31 will not have Week 56 evaluations.

Table 7. Visit Windows for Analysis of sPGA, PSS, DLQI, HAQ-DI, Pain VAS, Investigator's Global Assessment VAS, Patient's Global Assessment VAS, SJC, TJC, Laboratory Tests, and ECG in Part B (ITT/Safety Population)

Window Label	Target Day	Interval
Entry of Part B	1	≤ 1
Week 28	85	[2, 127]
Week 40	169	[128, 211]
Week 52	253	[212, 294 ^a]

Rx Day calculated relative to the first dose date on or after Week 16 for PBO/RZB_75 and PBO/RZB_150 arms, and relative to the date of Week 16 visit for RZB_75/RZB_75 and RZB_150/RZB_150 arms.

a. The minimum of upper bound and 105 days after the last dose.

Table 8. Visit Windows for Summary of Study Drug Injections in Part A

Window Label	Target Day	Time Window
Week 0	1	≤ 1
Week 4	29	[2, 57 ^a]

Rx Day calculated relative to the first dose date of study drug.

a. Before the first dose date on or after Week 16.

Table 9. Visit Windows for Summary of Study Drug Injections in Part B

Window Label	Target Day	Time Window
Week 16	1	≤ 1
Week 28	85	[2, 127]
Week 40	169	[128, 211]

Rx Day calculated relative to the date of first dose date on or after Week 16.

Definition of Missing Data Imputation

No global imputation is taking place at the database level. Efficacy related imputations are outlined in Section 10.0. There is no imputation for missing values in the safety analyses.

Rounding of Numeric Results

Rounding will be performed for presentation of results. No rounding will be performed before or during analyses. The ROUND function of SAS will be used to round results.

When dichotomizing continuous variables from single observations, associated continuous variables will be rounded to 9 decimal points before applying the cutoff point to determine the response status (for example, percent change from baseline in PASI score will be rounded to 9 decimal places before comparing to 90%).

The mean and median will be rounded for presentation to 1 decimal more than the data entered into the database. The standard deviation will be rounded to 2 decimal places more than the data entered into the database. The minimum and maximum values will be presented as entered into the database.

Probabilities will be rounded to 3 decimal places before assignment of statistical significance and will be presented in rounded format. Probabilities that round to zero or are reported by SAS as zero will be presented as "< 0.001." Probabilities that round to 1 or are reported by SAS as 1 will be presented as "> 0.999."

7.0 Demographics, Baseline Characteristics, Medical History, and Previous/Concomitant Medications

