7.7 DETERMINATION OF SAMPLE SIZE

The study is powered to show a benefit of BI 655066 over placebo in terms of PASI 90 response at Week 16. Based on the outcome from the trial 1311.2, the PASI 90 response rate at Week 16 is assumed to be at least 65% in the BI 655066 arm. There is only minimal data available on placebo response in the BI 655066 program but the phase 3 results from ustekinumab and secukinumab indicate a response rate for PASI 90 of approximately 5% in the placebo arm. With 2-sided significance level 5%, based on these assumptions (65% vs 5% PASI 90 response rates), 17 patients in the BI 655066 arm and 17 in the placebo arm will provide 95% power for each comparison and an overall power of at least 90%.

For the Japanese submission, the safety data of at least 100 Japanese patients exposed to BI 655066 at the registered dose(s) for 1 year or more is necessary for long team safety assessment as a result of the PMDA consultation meeting in 2015. This study will enrol a total of 168 patients, with 56 patients in each of the two BI 655066 arms and 56 patients in the placebo arm. It is expected that at least 68 patients exposed to BI 655066 75 mg and 68

Proprietary confidential information © 2017 Boehringer Ingelheim International GmbH or one or more of its affiliated companies

patients exposed to BI 655066 150 mg will reach at least 1 year exposure to BI 655066 in this clinical trial or in the following extension study. Other global phase III trials where Japanese patients are to be enrolled will make up for the remaining safety data requirements.

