9.0 Study Drug Exposure and Compliance

Summary of study drug treatment duration and compliance will be provided for each treatment arm in each treatment period under the ITT Population.

Study drug treatment duration (days) will be summarized using the sample size, mean, standard deviation, minimum, median and maximum. In addition cumulative exposure of RZB (including total patient years) will also be summarized in the ALL_RZB Population. Study drug treatment duration will be summarized as follows:

Study Drug Exposure (in Days) in Each Period:

Part A:

- For subjects who did not continue into Part B:
 - Date of last injection in Part A – Date of first injection in Part A + 84 days.
- For subjects who continued into Part B:
Minimum of
 - Date of first injection in Part B – Date of first injection in Part A
 - Date of last injection in Part A – Date of first injection in Part A + 84 days.

Part B:

Date of last injection in Part B – Date of first injection in Part B + 84 days.

ALL_RZB:

For study drug exposure during the administration of risankizumab in the ALL_RZB Population:

- Date of last injection of risankizumab – Date of first injection of risankizumab + 84 days.

A data cutoff date (December 15, 2017) will be applied during the interim analysis, and the duration of study drug exposure will be defined up to this cutoff date.

Compliance

There will be a summary of the number of subjects receiving study drug and dose at each study drug administration visit. This will be repeated on the cumulative number of doses.

When computing compliance at each study drug administration visit, the denominator will include all subjects in each analysis population who have not prematurely discontinued the study drug prior to the scheduled study drug injection. Subjects who have prematurely discontinued the study drug but have not prematurely discontinued the study are not used in the denominator.

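### No defined safety group brings together all patients given one risankizumab dose: ALL_RZB pools 75 mg and 150 mg, and the entire-study groups omit the placebo switchers

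*SAP*

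**What the plan says.** Table 1 in SAP section 5.1 defines four sets of groups:

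- Part A: RZB_75, RZB_150, PBO.
- Part B: RZB_75/RZB_75, RZB_150/RZB_150, PBO/RZB_75, PBO/RZB_150.
- Entire study: RZB_75/RZB_75 and RZB_150/RZB_150 only.
- ALL_RZB: a single code, "Subjects who received at least one dose of risankizumab 75/150 mg".

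The text assigns ALL_RZB to the key safety summaries (section 5.1) and to the tables of potentially clinically important laboratory values (11.3.2) and vital signs (11.4.2). Section 9.0 assigns it cumulative exposure: "In addition cumulative exposure of RZB (including total patient years) will also be summarized in the ALL_RZB Population". Adverse event rates per 100 patient-years (11.2.1) are specified for the entire study.

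Protocol section 7.7 bases the enrolled number on "the safety data of at least 100 Japanese patients exposed to BI 655066 at the registered dose(s) for 1 year or more". SAP section 4.3 repeats this and counts by dose: "It is expected that at least 68 patients exposed to risankizumab 75 mg and 68 patients exposed to risankizumab 150 mg" are to reach one year, in this trial or in the extension.

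**The concern.** The sample-size sections count patients by dose and need switchers to reach the count. The analysis sections never define the matching group. A reader who wants the safety experience of everyone given one dose finds two partial sources: an entire-study column without switchers and a Part B column with switchers only. The one group that contains everyone mixes the doses.

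If one dose is registered, the cumulative exposure for ALL_RZB describes a mixture of that dose and another. The by-dose patient-year rates leave out up to a third of the patients assigned to each dose. At stake is how fully the trial's main safety product, exposure at a given dose, is reported. No efficacy estimate or test is affected.

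**Working it through.** **1. Is the trial's size driven by safety?** Protocol 7.7 assumes PASI 90 rates of 65% and 5%, a two-sided 5% level and 95% power per comparison, and states 17 per arm. Check:

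- n = [1.960·√(2·0.35·0.65) + 1.645·√(0.65·0.35 + 0.05·0.95)]² / 0.60² = (1.322 + 0.863)² / 0.36 = 13.3, so 14 per arm without continuity correction.
- With continuity correction: (13.26/4)·[1 + √(1 + 4/(13.26·0.60))]² = 16.4, so **17 per arm**. The stated figure is reproduced.

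Fifty-six per arm is therefore not needed for efficacy. It comes from the exposure requirement.

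**2. Patients per dose.** The ratio 2:2:1:1 applied to 168 gives 56, 56, 28 and 28.

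- Assigned to each dose: 56 + 28 = 84.
- Largest by-dose group in Table 1: 56. Left out: 28/84 = 33%.
- Switchers needed to reach 68: 68 − 56 = at least 12.
- Share of the 84 that must reach one year: 68/84 = 81%.

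**3. Where each patient appears (75 mg; 150 mg is the same).**

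| Group set | From Week 0 (56) | Switchers (up to 28) | Doses separate? |
|---|---|---|---|
| Part A | yes | as placebo | yes |
| Part B | yes, if they continue | yes, own column | yes |
| Entire study | yes | no | yes |
| ALL_RZB | yes | yes | no |

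No row has both kinds of patient in one column for one dose.

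**4. Exposure.** The SAP 9.0 rule is last minus first injection plus 84 days. By the protocol dosing table (4.1.4), the first risankizumab injection is at Week 0 or Week 16 and the last at Week 40. For nominal completers, with all placebo patients entering Part B:

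- From Week 0: 280 + 84 = 364 days (52 weeks). 56 × 364/365.25 = 55.8 patient-years.
- Switchers: 168 + 84 = 252 days (36 weeks). 28 × 252/365.25 = 19.3 patient-years.
- Total per dose: 75.1, and 19.3/55.8 = +35%.

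Section 11.2.1 uses 105 days in place of 84 for the rate denominator. That gives 56 × 385/365.25 = 59.0 and 28 × 273/365.25 = 20.9 patient-years, again about +35%.

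**5. What the extra exposure buys.** The one-sided 95% upper bound with zero events is 1 − 0.05^(1/n). The chance of at least one event at 2% risk is 1 − 0.98^n. Switchers are followed for less time, so 84 patients should not be counted as 84 full follow-ups. Scaling to patient-years under a constant hazard gives n = 56 × 75.1/55.8 = 75.4.

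| n | Upper bound | Chance of ≥1 event |
|---|---|---|
| 56 (entire-study group) | 5.2% | 68% |
| 75.4 (combined, scaled) | 3.9% | 78% |
| 84 (combined, unscaled) | 3.5% | 82% |

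The unscaled row overstates the gain. For the pool of 168 the unscaled bound is 1.8%, but that applies to the two doses together and to neither alone.

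**The case against.** The strongest reply is that dose-specific safety is already planned. Part A compares each dose with placebo, Part B shows all four sequences, and the entire-study groups are by dose. For a switcher, Part B is the whole risankizumab exposure in this trial. The entire-study column and the Part B switcher column are therefore disjoint, and subject counts can be added. Section 9.0 also summarises treatment duration by arm and period with sample size and mean, so patient-years follow by multiplication.

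Most of this stands, and it rules out three stronger readings.

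- *That a dose-related signal is hidden.* Risks of, say, 3% and 9% would show as 6% in equal-sized halves of ALL_RZB, but the by-dose tables would still display the contrast.
- *That no table at all will show everyone given a dose.* The table list announced as SAP section 17 is not in the text available here, so such a table cannot be excluded. The point concerns Table 1 and the SAP text.
- *That by-dose columns would demonstrate the 68 per dose.* Switchers reach about 36 weeks here. The one-year count relies on the extension, and other global trials supply the rest of the safety requirement.

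It is also fair that the requirement speaks of dose(s). If both were registered, the pool would be informative.

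The reply does not cover the rates. Their numerator counts events (one per preferred term, day and subject), whereas the by-period tables count subjects. The rates are specified for the entire study, whose groups exclude switchers. A by-dose rate that includes switchers cannot be rebuilt from the tables described.

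**Conclusion.** The point holds as a gap in defined groups, not as missing dose information. Table 1 and the available SAP text contain no group combining all patients given one dose. By-dose patient-year rates leave out up to 28 of 84 patients. Cumulative risankizumab exposure is specified only for the two doses together, although the trial was sized on exposure at the registered dose(s) and counts by dose.

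Closing the gap adds about 35% to the dose-specific exposure and moves the zero-event bound from 5.2% to about 3.9%. These figures assume nominal completion, every placebo patient entering Part B and a constant hazard; dropout would lower the patient-years. This is a worthwhile reporting change and does not threaten the trial's conclusions.

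**What to change.** Keep the pooled ALL_RZB column and add ALL_RZB_75 and ALL_RZB_150 (up to 84 patients each) to Table 1. Use them in the ALL_RZB exposure summary, the key adverse event summaries, and the potentially clinically important laboratory and vital-sign tables. Present adverse event rates per 100 patient-years for these columns beside the percentages.

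State the assignment rule: the risankizumab dose actually received, with any patient given both doses flagged. Neither existing rule serves. Section 5.1 analyses safety by treatment received at the randomisation visit, which for switchers is placebo. Randomised sequence alone would misplace the wrong-treatment or incorrect-dose deviations that section 7.4 foresees.

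The cost is two columns in planned tables. Section 6.0 already gives ALL_RZB its own baseline and final-observation rules, so no new data are needed, and alpha and the primary analysis are untouched. The drawback is that crude percentages in the new columns mix about 52 and about 36 weeks of exposure, which is why the patient-year rates must stand next to them.
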